Appendix 7 Immune-Related Response Criteria

INTRODUCTION

Increasing clinical experience indicates that traditional response criteria (e.g., Response Evaluation Criteria in Solid Tumors [RECIST] and World Health Organization [WHO]) may not be sufficient to characterize fully activity in the new era of target therapies and/or biologics. In studies with cytokines, cancer vaccines, and monoclonal antibodies, complete response, partial response, or stable disease has been shown to occur after an increase in tumor burden as characterized by progressive disease by traditional response criteria. Therefore, conventional response criteria may not adequately assess the activity of immunotherapeutic agents because progressive disease (by initial radiographic evaluation) does not necessarily reflect therapeutic failure. Long-term effect on the target disease must also be captured. The immune-related response criteria¹ (irRC) are criteria that attempt to do that by enhancing characterization of new response patterns that have been observed with immunotherapeutic agents (i.e., ipilimumab). (Note: The irRC only index and measurable new lesions are taken into account.)

GLOSSARY

Term	Definition
SPD	Sum of the products of the two largest perpendicular diameters
Tumor burden	$SPD_{\text{index lesions}} + SPD_{\text{new, measurable lesions}}$
Nadir	Minimally recorded tumor burden
irCR	Immune-related complete response
irPR	Immune-related partial response
irSD	Immune-related stable disease
irPD	Immune-related progressive disease
irBOR	Immune-related best overall response

BASELINE ASSESSMENT USING irRC

Step 1. Identify the index lesions (five lesions per organ, up to ten visceral lesions and five cutaneous lesions).

¹ Wolchok JD, Hoos A, O'Day S, et al. Guidelines for the evaluation of immune therapy activity in solid tumors: immune-related response criteria. Clin Can Res 2009;15:7412–20.

Appendix 7 Immune-Related Response Criteria (cont.)

Step 2. Calculate the SPD of all of these index lesions:

$$SPD = \sum_i (\text{Largest diameter of lesion } i) \times (\text{Second largest diameter of lesion } i).$$

POST-BASELINE ASSESSMENTS USING irRC

Step 1. Calculate the SPD of the index lesions.

Step 2. Identify new, measurable lesions ($\geq 5 \times 5$ mm; up to five new lesions per organ: five new cutaneous lesions and ten visceral lesions).

Step 3. Calculate the SPD of the new, measurable lesions.

Step 4. Calculate the tumor burden:

$$\text{Tumor burden} = SPD_{\text{index lesions}} + SPD_{\text{new, measurable lesions}}$$

Step 5. Calculate the change in tumor burden relative to baseline and the change in tumor burden relative to nadir.

Step 6. Derive the overall response using the table below.

Overall Response	Criterion
irCR	Complete disappearance of all lesions (whether measurable or not, and no new lesions) confirmed by a repeat, consecutive assessment ≥ 4 weeks from the date first documented
irPR	Decrease in tumor burden $\geq 50\%$ relative to baseline confirmed by a consecutive assessment ≥ 4 weeks from the date first documented
irSD	Criteria for irCR, irPR, and irPD are not met; does not require confirmation
irPD	Increase in tumor burden $\geq 25\%$ relative to nadir confirmed by a consecutive assessment ≥ 4 weeks from the date first documented

irCR=immune-related complete response; irPD=immune-related progressive disease;
irPR=immune-related partial response; irSD=immune-related stable disease.

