4.5.5.2 Response Criteria

All tumors will be evaluated for disease response and progressive disease with RECIST v1.1 (see [Appendix 6](#)) with the exception of those listed below.

- Neuroblastoma: *m*INRC (see [Appendix 3](#))
- Hodgkin's lymphoma and non-Hodgkin's lymphoma: Revised Response Criteria for Malignant Lymphoma (see [Appendix 4](#))
- ATRT: RANO criteria (see [Appendix 11](#))

Patients with synchronous ATRT and rhabdoid tumor with no clear primary should be enrolled into the rhabdoid tumor cohort. These patients' tumors will be evaluated with RECIST v1.1 criteria.

Patients who enroll with evaluable but not measurable disease will have a modified response assessment. For such patients, partial response cannot be determined; therefore, response will be limited to complete response, stable disease, or progressive disease.

During treatment, patients who show evidence of clinical benefit will be permitted to continue atezolizumab treatment after criteria for progressive disease for their specified response assessment are met, if they meet all of the following criteria:

- Evidence of clinical benefit as assessed by the investigator and agreed upon by the Medical Monitor
- Absence of symptoms or signs (including worsening laboratory test values) indicating unequivocal progression of disease
- No decline in Lansky or Karnofsky Performance Status that can be attributed to disease progression
- Absence of tumor progression at critical anatomical sites (e.g., leptomeningeal disease) that cannot be managed by protocol-allowed medical interventions

Patients and/or their parents or guardians must sign a consent acknowledging treatment continuation after possible worsening disease in order to continue to receive atezolizumab. Patients for whom radiographic disease progression is confirmed at a subsequent tumor assessment may be considered for continued study treatment at the discretion of the investigator if they have evidence of clinical benefit and continue to meet the criteria above. If an individual patient continues to experience clinical benefit beyond 2 years of radiologic progressive disease (see Section 3.3.4), the Sponsor and treating physician will apply for additional approval from health authorities for continued treatment.

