4.6.2 Study Drug Discontinuation

Patients must discontinue study drug if they experience any of the following:

- Symptomatic deterioration attributed to disease progression as determined by the investigator after integrated assessment of radiographic data, biopsy results, and clinical status
- Unacceptable toxicity despite per-protocol treatment interruptions
- Pregnancy
- Withdrawal of consent
- Interruption of study treatment for >105 days (*e.g., more than 105 days between infusions*) because of an atezolizumab-related adverse event, except in patients who must be tapered off corticosteroids used to treat adverse events (see Section 5.1.1.1 for details). This duration may be extended after consultation with the Medical Monitor.

Patients who discontinue study drug for any reason will be asked to return to the clinic for a study drug discontinuation visit and undergo follow-up assessments (see the schedule of assessments in [Appendix 1](#)). If treatment with another anti-cancer treatment is scheduled to begin within 90 days after the last dose of atezolizumab, assessments at this visit should be performed before the patient starts the other treatment, if possible. Patients who discontinue for reasons other than progressive disease should continue follow-up assessments, including tumor assessments, using the long-term follow-up schedule (*e.g., every 3 months for the first 2 years, every 6 months during Year 3, etc.*) until radiographic documentation of progressive disease, they start another treatment, or consent is withdrawn. For patients who continue receiving study drug beyond radiographic progressive disease, assessments should be continued until they stop taking study drug. The primary reason for study drug discontinuation should be documented on the appropriate eCRF.

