Appendix 1 Schedule of Assessments (cont.)

Day	Screening Period ^a	Treatment Period															Follow-Up Period ^b		
		C1			C2		C3	C4	C5	C6	C7	C8	C9	C10	C11	C12+	Study Drug Discont. ^c	Day 90 Follow-up ^c	Long-Term Follow-Up ^d
	1	8	15	1	ATRT Only		1	1	1	1	1	1	1	1	1				
	-28 to -1																		
Coagulation (INR, aPTT, PT)	x																		
Amylase/lipase ^q	x				x				x		x		x		x		x	x	
Thyroid function testing ^r	x				x				x		x		x		x		x	x	
Virology testing ^s	x																		
PK/ATA blood samples ^t		x	x		x			x	x				x				x	x	x ^u
Whole blood for TBNK		x						x									x	x ^u	
Whole blood for biomarkers ^t		x			x			x					x				x	x ^u	
Plasma for biomarkers ^t		x			x			x					x				x	x ^u	
Tumor assessments ^{v, w}	x				x				x		x		x				x	x ^w	x ^w
Atezolizumab administration ^x		x			x			x	x	x	x	x	x	x	x	x			
Concomitant medications ^y	x	x	x	x	x	x	x	x	x	x	x	x	x	x	x	x	x	x	x
Adverse events	x	x	x	x	x	x	x	x	x	x	x	x	x	x	x	x	x	x	x

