- ^u Collect sample between 90 to 150 days after last dose of study drug.
- ^v The same *imaging technique(s) and procedure(s)* (CT, MRI, FDG-PET, *and/or* MIBG scan) used to assess disease sites at screening should be used throughout the study (e.g., the same contrast protocol for CT scans). To the extent that is feasible, assessments should be performed by the same evaluator to ensure internal consistency across visits. See Section 4.5.5 for detailed information on tumor and response evaluations.
- ^w Tumor assessments must be performed during the last week of Cycles 2, 4, 6, and 8 and every 4th cycle thereafter (i.e., within 7 days prior to Day 1 of the next cycle). At the investigator's discretion, tumor assessments may be repeated at any time if progressive disease is suspected. An objective response should be confirmed by repeat assessments ≥ 4 weeks after initial documentation. Patients who discontinue study drug without progressive disease should continue follow up assessments, including tumor assessments, using the long-term follow up schedule (e.g., every three months for the first 2 years, every 6 months during year 3, etc.) until radiographic documentation of progressive disease, they start another treatment or consent is withdrawn. Patients who continue to receive study drug beyond radiographic progressive disease should continue follow-up assessments until they stop taking study drug.

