Appendix 4 Revised Response Criteria for Malignant Lymphoma (cont.)

Timepoint Response

Target Lesions	Non-Target Lesions	New Lesions ^a	Timepoint Response
CR	CR	No	CR
CR	SD	No	PR
CR	UE	No	UE
PR	UE	No	UE
PR	CR	No	PR
PR	SD	No	PR
SD	UE	No	UE
SD	CR	No	SD
SD	SD	No	SD
PD	Any	Yes/No	PD
Any	PD	Yes/No	PD
Any	Any	Yes	PD
UE	Non-PD	No	UE
UE	UE	No	UE
CR	NA ^c	No	CR
PR	NA ^c	No	PR
SD	NA ^c	No	SD
NA ^b	SD	No	SD
NA ^b	CR	No	CR
NA ^b	UE	No	UE
NA ^b	NA ^c	No	UE

CR=complete response; NA=not applicable; PD=progressive disease; PR=partial response; SD=stable disease; UE=unable to evaluate.

Note: Modified from Cheson BD, Pfistner B, Juweid ME, et al. Revised response criteria for malignant lymphoma. J Clin Oncol 2007;25:579–86.

^a Identification of new lesions at a post-baseline time point will result in a response assessment of PD. If an identified new lesion subsequently becomes UE, the timepoint response will be recorded as PD unless the new lesion has proven to have resolved.

^b No target lesions identified at baseline.

^c No non-target lesions identified at baseline.

Appendix 4

Revised Response Criteria for Malignant Lymphoma (cont.)

Response should be determined on the basis of radiographic and clinical evidence of disease. For the end-of-treatment response assessment, an FDG-PET will be performed 6–8 weeks after the last study treatment. Assessment of PET should follow the criteria described by Juweid et al. 2007, which is presented in the table Response Definitions for Clinical Trials.

COMPLETE RESPONSE

- Complete disappearance of all detectable clinical evidence of disease and disease-related symptoms if present before therapy
- Typically ¹⁸F-fluorodeoxyglucose (FDG)–avid lymphoma: in patients with no pre-treatment positron emission tomography (PET) scan or when the PET scan was positive before therapy, a post-treatment residual mass of any size is permitted as long as it is PET negative.
- Variably FDG-avid lymphomas/FDG avidity unknown: in patients without a pre-treatment PET scan, or if a pre-treatment PET scan was negative, all lymph nodes and nodal masses must have regressed on CT to normal size (≤ 1.5 cm in their greatest transverse diameter for nodes > 1.5 cm before therapy). Previously involved nodes that were 1.1 to 1.5 cm in their long axis and > 1.0 cm in their short axis before treatment must have decreased to ≤ 1.0 cm in their short axis after treatment.

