c. Special Notes on Response Assessment

When nodal disease is included in the sum of target lesions and the nodes decrease to “normal” size (< 10 mm), they may still have a measurement reported on scans. This measurement should be recorded even though the nodes are normal in order not to overstate progression should it be based on increase in size of the nodes. As noted earlier, this means that patients with CR may not have a total sum of “zero” on the eCRF.

Patients with a global deterioration of health status requiring discontinuation of treatment without objective evidence of disease progression at that time should be reported as “symptomatic deterioration.” Every effort should be made to document objective

Appendix 6

Response Evaluation Criteria in Solid Tumors: Modified Excerpt from Original Publication (cont.)

progression even after discontinuation of treatment. Symptomatic deterioration is not a descriptor of an objective response; it is a reason for stopping study therapy. The objective response status of such patients is to be determined by evaluation of target and non-target disease as shown in [Tables 1–3](#).

For equivocal findings of progression (e.g., very small and uncertain new lesions; cystic changes or necrosis in existing lesions), treatment may continue until the next scheduled assessment. If at the next scheduled assessment progression is confirmed, the date of progression should be the earlier date when progression was suspected.

If a patient undergoes an excisional biopsy or other appropriate approach (e.g., multiple passes with large core needle) of a new lesion or an existing solitary progressive lesion that following serial sectioning and pathological examination reveals no evidence of malignancy (e.g., inflammatory cells, fibrosis, etc.), then the new lesion or solitary progressive lesion will not constitute disease progression.

In studies for which patients with advanced disease are eligible (i.e., primary disease still or partially present), the primary tumor should also be captured as a target or non target lesion, as appropriate. This is to avoid an incorrect assessment of CR if the primary tumor is still present but not evaluated as a target or non-target lesion.

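### An unconfirmed irPD defaults to irSD, and no confirming scan is clearly required for neuroblastoma patients who stop at first progression, so supportive irRC PFS and DOR are expected to look too favorable

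*Combined protocol and SAP*

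**What the plan says.** Sections 3.4.4 and 6.6.2 use irRC for secondary ORR, PFS and DOR in neuroblastoma, Hodgkin's lymphoma and non-Hodgkin's lymphoma, with the same methods as the main analyses. Under Section 6.6.1, PFS without an event is therefore censored at the last assessment showing the patient progression-free, and death is an event. DOR follows the same rule.

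In Appendix 7, irPD is a rise in tumor burden of at least 25% "relative to nadir confirmed by a consecutive assessment" at least 4 weeks after it was first documented. irSD is the default: "Criteria for irCR, irPR, and irPD are not met; does not require confirmation". Nothing says how to count a rise that is never re-imaged.

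On imaging after progression:

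- **Section 4.5.5.1** makes a rescan mandatory for patients treated past progression.
- **Section 3.3.4** only recommends confirming progression.
- **Section 4.6.2:** "Patients who discontinue for reasons other than progressive disease should continue follow-up assessments, including tumor assessments, using the long-term follow-up schedule". The same section asks patients who discontinue for whatever reason to attend the discontinuation visit and have the Appendix 1 follow-up assessments.
- **Appendix 1** marks tumor assessments at Day 90 and in long-term follow-up. Those cells carry note w: "Patients who discontinue study drug without progressive disease should continue follow up assessments". Note c sets the discontinuation visit within 28 days of the last dose and lets it be the visit at which progression is found.
- **Appendix 4**, lymphoma only: "For the end-of-treatment response assessment, an FDG-PET will be performed 6–8 weeks after the last study treatment".

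**The concern.** A rule that needs a second scan works only if the second scan happens. If a patient stops at the first rise and is not imaged again, the text does not call that rise progression; it calls it irSD. Some of these patients will be clear progressors, because one of Section 4.5.5.2's conditions for continuing past progression is "Absence of symptoms or signs (including worsening laboratory test values) indicating unequivocal progression of disease". They would then count as progression-free until death, or be censored at a point related to how badly they were doing. A favorable irRC PFS set beside the primary PFS could be taken for an immune-type benefit when part of it comes from missing confirmation. Two analysts could also follow this text and report different irRC results, since the censoring date could be the scan showing the rise or the one before it.

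**Working it through.** The plan gives no figure on this point, so there is none to reproduce. The check has two parts.

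**1. Which scans could confirm a rise?** Scheduled scans fall in the last week of a 21-day cycle (Section 4.5.5.1), that is 14–20 days after the last dose. A confirming scan must come at least 28 days later.

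| Later assessment | Days after last dose | Gap from PD scan | Confirms? |
|---|---|---|---|
| Rescan if treatment continues | – | about 42 days (2 cycles) | Yes, but only for patients who continue |
| Discontinuation visit | up to 28 | at most 28 − 14 = 14 days; may be the same visit | No |
| Day 90 (± 10) visit | 80–100 | 80 − 20 = 60 to 100 − 14 = 86 days | Yes, if it is due |
| Lymphoma FDG-PET | 42–56 | 42 − 20 = 22 to 56 − 14 = 42 days | Usually |

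For the PET, 7 scan days × 15 PET days = 105 pairs, of which 84 (80%) reach 28 days. Appendix 1 does not schedule this PET, and PET alone may not give the two-dimensional measurements that irRC needs. For neuroblastoma, everything turns on whether Day 90 imaging applies after a stop for progression. If it does, the gap narrows to patients with no usable Day 90 scan. One example is a patient whose new therapy began first: under note c, a visit after that point needs only blood samples.

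**2. How far could the estimate move?** Assumptions, none from the documents: exponential time to progression with median 10 weeks; survival after progression with median 12–40 weeks; 78 weeks of follow-up; every first progression meets the 25% threshold. Scans are read at Weeks 6, 12, 18 and 24, then every 12 weeks. A share f stops unconfirmed, with an event at death or, if alive at 78 weeks, censoring at the PD scan.

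Reference (first rise counts): 24-week rate = 2^(−24/10) = 0.189, or 19%.

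Hand check for post-progression median 12 weeks, measuring survival from the PD scan and ignoring the few censored patients:

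- Progression first read at Weeks 6, 12, 18, 24: probabilities 0.340, 0.224, 0.148, 0.098.
- Alive at Week 24 given each: 2^(−18/12) = 0.354, 2^(−12/12) = 0.500, 2^(−6/12) = 0.707, 1.
- Sum of products = 0.435.
- Literal rate at f = 0.25: 0.189 + 0.25 × 0.435 = 0.298. At f = 0.50: 0.189 + 0.50 × 0.435 = 0.407.

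Simulation (200,000 patients per setting, post-progression median 12 to 40 weeks):

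| Share stopping unconfirmed | 24-week rate | Median (weeks) |
|---|---|---|
| 0% | 19% | 12 |
| 10% | 23–24% | 12 |
| 25% | 30–33% | 18 |
| 50% | 40–48% | 20–24 |

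The medians are jumps on the scan grid. With a latent median of 8 weeks, the median stays at 12 weeks at f = 25%. The large-sample 24-week rate also rises if censoring is moved to the scan before the rise.

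For lymphoma, f = stop share × (1 − 0.8 × share of PETs usable). A 50% stop share with every PET usable gives 0.50 × 0.2 = 10% unconfirmed, so little movement. DOR was not simulated; only its direction is argued.

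**The case against.** **Confirmation is the purpose of irRC.** Appendix 7 itself says initial radiographic progression need not mean treatment failure. Counting an unconfirmed rise therefore moves the endpoint towards a first-rise definition, and which rule leads is a choice of estimand. This stands as a limit: too favorable here means relative to counting the first documented rise. It does not justify leaving irSD as the silent default for patients who are never re-imaged.

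**A reader might infer that the plan requires no confirming scan at all.** The documents do not settle that. Section 4.6.2 sends everyone who discontinues to the Appendix 1 follow-up, and note w directs patients without progression to the long-term schedule without expressly exempting the others from Day 90.

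**A reader might infer that the unconfirmed patients are mainly true progressors.** Section 4.5.5.2 shows that some will be, but gives no share.

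**A reader might infer that the bias always runs upward.** With censoring at the PD scan, a check of 3,000 simulated cohorts of 10 found no exception at any time point. With censoring at the earlier scan, an upward shift is not guaranteed at every time point, though the large-sample 24-week rate still rose.

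**Dating a confirmed irPD is largely implied already**, by the first-occurrence wording in Section 6.6.1 and the first-documented date in Appendix 7. Appendix 6 says it outright ("If at the next scheduled assessment progression is confirmed, the date of progression should be the earlier date when progression was suspected") where Appendix 7 does not, so this part needs only a clarifying line.

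**irRC fits neuroblastoma imperfectly.** Progression seen only in marrow, MIBG or non-target lesions is outside irRC, and neither the concern nor the fix reaches it.

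**Conclusion.** The point holds in a limited form. Appendix 7 states a rule, and the follow-up text does not clearly supply the scan that the rule depends on for neuroblastoma patients who stop at first progression. Lymphoma is partly covered. The expected direction is upward for irRC PFS, and for irRC DOR among responders. The size cannot be derived from the documents: the stop share, time to progression and later survival are all assumed. The 24-week figures are an illustration, and specific median shifts should not be quoted as findings.

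Sampling noise is also large. With no bias, the simulated 95% range of the median is 6–24 weeks at n = 10–14 and 6–18 weeks at n = 40.

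Primary PFS, irRC ORR and the Table 3 expansion counts are unaffected, and no hypothesis test is planned. A reader might infer that the trial's main efficacy conclusions are at risk; they are not. What is at risk is a supportive estimate. The repair is cheap and should be made.

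**What to change.** In Section 6.6.2 and Appendix 7, for irRC PFS and DOR:

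1. Count a first increase of at least 25% from nadir as irPD on the date first documented when there is no later evaluable assessment at least 4 weeks on and before new anti-cancer therapy. A lymphoma end-of-treatment assessment that yields irRC measurements qualifies as such an assessment.
2. Let a later assessment of that kind which does not confirm the rise reverse it.
3. State explicitly that a confirmed irPD takes the first date.
4. Report the literal confirmed-only rule as a sensitivity analysis, with its censoring date stated.

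Separately, reconcile Section 4.6.2, Appendix 1 (the Day 90 mark, notes c and w) and Appendix 4 on imaging after a stop for progression. Which of these should govern is for the sponsor to settle.

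Cost: analysis wording and one reconciliation of existing text, with no new scans. A few pseudoprogressors who stop early will count as irPD and the irRC estimates will look less favorable; the sensitivity analysis shows by how much.
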